Quantifying Energetic Demands of Walking for People with Cerebral Palsy

NCT #: NCT04303078

Date: November 3, 2025

STUDY PROTOCOL

Background

Walking promotes independence, participation, fitness, and exploration in daily life. Like other activities, walking requires metabolic energy. That energy is obtained from the food we eat and the air we breathe, ultimately being used by our muscles to power movement. Experimentally, we can measure the energy being used by our muscles using indirect calorimetry, which monitors oxygen consumption and carbon dioxide generation as the body converts stored energy into the form used by muscles during activities of daily living. Decades of energetics research has demonstrated that human walking is incredibly efficient. However, for people with cerebral palsy, the energetic cost of walking is significantly increased, on average over two times higher than for typically-developing individuals. This means that for people with cerebral palsy, walking is as demanding as jogging or climbing stairs. Energetic costs of this magnitude restrict activities of daily living and causes exhaustion. While our team and many others have sought to reduce these costs through surgical interventions, rehabilitation, orthotics, or other assistive devices, these strategies have not resulted in meaningful reductions in energy. To design strategies that successfully reduce walking costs, we must first understand the underlying mechanisms contributing to elevated cost in people with cerebral palsy. This clinical trial seeks to fill this knowledge gap by examining biomechanical factors that contribute to elevated energetic costs of walking for people with cerebral palsy. Specifically, we will evaluate the energetic cost of vertical and lateral support of the body during walking for children with cerebral palsy, and compare these costs to typically-developing peers. Supporting and stabilizing the body require very little energy during unimpaired walking, accounting for less than ten percent of the total walking cost. However, the relative costs of these tasks remain unknown for people with cerebral palsy, which is problematic as they can have direct implications for treatment decisions and assistive device design. This research uses a mechatronic device to provide precise support and stabilization assistance during walking, so that we can quantify the impact of this assistance on walking cost. This research provides the foundation to create evidence-based strategies to decrease energy costs, minimize fatigue, and increase quality of life for people with cerebral palsy and other neurologic injuries.

Human Subjects Involvement, Characteristics, and Design

Aims 1 and 2 will use the same set of individuals to evaluate if energetic cost changes with varying levels of support. We aimed to recruit at least 21 individuals with cerebral palsy and 7 age- and sex-matched typically-developing peers (3:1 allocation ratio) to participate in the proposed research at Gillette Children's Specialty Healthcare. The age range of 8 to 17 years will allow us to examine costs during the period most children receive treatment and evaluate potential differences due to age. Our inclusion criteria are age between 8 and 17 years, diagnosis of spastic bilateral cerebral palsy, classification as Gross Motor Function Classification System Level II, absence of dystonia or ataxia or athetosis, no surgical procedures within the preceding 12 months, no pharmacological spasticity treatments such as botulinum toxin or baclofen within two months prior to testing, no current pharmacological agents that impact neuromuscular control, capacity to follow instructions and provide informed assent, ability to walk on a treadmill for six minutes, and absence of acute or chronic pain in lower extremities. Individuals will not be excluded on the basis of ethnic background, race, sex, or socioeconomic factors.

Each individual will perform a protocol that consists of walking on a treadmill with varying levels of support while energy cost is measured by indirect calorimetry. An experienced pediatric physical therapist will collect physical exam data including strength, selective motor control, spasticity, and joint range of motion. We will place wireless electromyography sensors on each leg to monitor the seven large superficial muscle groups that have previously been shown to be important contributors to walking biomechanics. The electromyography data will be collected at 2000 Hertz, band-pass filtered at 20 to 450 Hertz, rectified, and low-pass filtered at 20 Hertz to compare between levels of support or stabilization. We will employ a standard clinical marker set and model to calculate kinematics using the Vicon plug-in-gait model, including functional calibration of knee and hip joints. Participants will wear shoes without orthoses during all trials.

We will use indirect calorimetry to calculate net dimensionless walking cost. Energetic cost is defined as the energy consumed per unit time. We will measure resting cost while the participant is supine in a recliner for five minutes. Walking cost will be measured while walking at each level of support or stabilization assistance. Resting and walking costs are evaluated by measuring the volume of oxygen consumed and carbon dioxide produced over the last three minutes of each five minute walking trial.

We will familiarize each participant to walking on the instrumented treadmill before beginning the walking trials. In our extensive experience with treadmill testing, we find this usually takes less than five minutes for children with cerebral palsy. Participants will then complete the walking trials to quantify support or stabilization costs, with order randomized between levels of assistance and a minimum twenty-minute break between support and stabilization trials. All participants will walk at a fixed dimensionless speed of 0.26 to account for differences in size between participants. We selected this dimensionless speed to provide a common and achievable speed based on prior trials of children classified as Gross Motor Function Classification System Level II who have completed energetic testing at Gillette. There will be a rest between trials. We will ask participants to report perceived exertion after each trial.

For both aims, we will use a custom mechatronic system with forces generated by a Humotech system that enables control of vertical or lateral forces to the body during walking. The mechatronic system allows us to precisely generate and monitor desired forces while minimizing undesired forces throughout the trial. For Aim 1 we control the direction of the applied vertical force using a low friction and low inertia 2 degree-of-freedom ceiling-mounted gantry. For Aim 2,

we apply lateral forces when the pelvis deviates from the middle line of the treadmill using a custom-designed frame that allows for free movement of the pelvis in the fore/aft direction.

a. Potential risks:

There are minor risks associated with completing motion analysis and indirect calorimetry while walking on a treadmill with the mechatronic system. The potential risks associated with the proposed research include risk of tripping or falling while standing and walking on a treadmill, risk of skin discomfort from sensors attached to the skin to monitor muscle activity with electromyography sensors and motion with reflective markers, risk of fatigue and soreness from the exercise activity of walking, risk from applied assistance as the Humotech system applies force to a safety harness to provide vertical and lateral forces, and risk of privacy breach. Tripping and falling are possibilities and we will take numerous precautions to prevent such risk as described below. Fatigue and muscle soreness are also potential risks and we will provide adequate time to rest and recover for all tasks. Forces from the Humotech system are also a potential risk and physical hardware and software back-up safety mechanisms were built into the system to reduce the risk of excessive forces.

b. Recruitment and informed consent:

Children with cerebral palsy will be recruited from Gillette Children's Specialty Healthcare using brochures designed to describe the research and involvement. An experienced research coordinator will assist with recruiting and contacting potential participants. Before participation, each child and their parent or guardian will receive a thorough explanation of the protocols from a member of the research team. We will obtain informed permission from the parent or guardian and assent from the child. Children that do not voluntarily communicate their assent and understand the procedures will not be included in the study. Information will be provided verbally and in writing. Individuals will be reassured of their right to withdraw at any time from the study.

c. Protection against risks:

We take numerous precautions to protect against risks associated with using motion capture to analyze human movement. To prevent tripping and falling we ensure that the floor of the facility and treadmill is free from wires or other obstructions and a safety harness is used while walking on the treadmill. Electromyography sensors and motion analysis markers are also safe and have been tested and used extensively during similar tasks for research and clinical applications. For the Humotech system, to avoid accidents due to applying external assistance, the connections to the harness include automatic releases if the force from the system exceeds a threshold or if the position of the actuator exceeds normal operating limits. Emergency stop buttons are provided to the participant and research staff that will immediately stop the treadmill and force actuator. We will inspect all wires, equipment, and connections before every experiment. Participants will be given frequent breaks during all experiments to avoid fatigue. For all experiments, individuals can terminate the experiment at any time. To protect against any breach in confidentiality, data collected for this study will be stored securely on password-protected computers. Codes instead of names of individuals will be used on all data files and reports. Any data used for publication or presentations will be de-identified.

This research involves children who represent a vulnerable population. According to age, assent or consent will be provided by each child in addition to consent from the parent or guardian.

Participants will be reminded throughout the research that they can stop participation. Additional protections include minimal use of adhesives for placing markers on the skin, size adjustable safety harnesses, and the use of exertion scales to monitor participant comfort and energy throughout the experimental protocol. The parent or guardian will be allowed to stay with the child throughout all testing procedures.

d. Potential benefits of the proposed research to human subjects and others:

There are no immediate potential benefits to the participants in this study.

e. Importance of the knowledge to be obtained:

The potential risks associated with this study are reasonable in the context of the knowledge and advancement in our understanding of cerebral palsy that will be gained. We anticipate that the proposed experiments will provide fundamental insight into the mechanisms underlying elevated energetic cost during walking for children with cerebral palsy relative to typically-developing peers. This research will test the generalizability of our current theory for understanding how humans efficiently move and explore the world, which are critical for activity and participation. Understanding the generalizability of this theory is critical to enhance our ability to support life-long participation and support human performance across the range of human health and ability. This basic-science proposal will provide the foundation for future research that can support novel strategies to manage the energetic costs of walking and enable participation across the lifespan for individuals with or without cerebral palsy. The results from this work will also be extendable to other clinical populations such as stroke, traumatic brain injury, spinal cord injury, and multiple sclerosis, which also exhibit similar pathology and elevated energetic costs of movement.

STATISTICAL ANALYSIS

We will recruit children with bilateral cerebral palsy who are classified as Gross Motor Function Classification System Level II and typically-developing peers. Our sample size was designed to test the primary hypotheses that support and stabilization costs are elevated for children with cerebral palsy relative to typically-developing peers. Independent sample t-tests will be used to compare the support and stabilization costs between groups. Given the novelty of this work, we have based these estimates of our effect size on our retrospective studies and literature, where available. We estimated an effect size of 1.5 based on three comparisons. First, Unnithan et al., (2006) observed support costs in children with cerebral palsy more than two times that reported in unimpaired individuals, although the amount of assistance was not reported nor systematically controlled¹. Second, prior experiments with unilateral amputees and stroke survivors, who generally have reduced energetic costs compared to children with cerebral palsy, showed elevated support and stabilization costs. Third, the difference in fixed cost between children with cerebral palsy and typically-developing peers from our retrospective analyses supports this effect size. To detect an effect size of 1.5 with alpha equal to 0.05 and an allocation ratio of cerebral palsy to typically-developing of three to one would require 21 children with cerebral palsy and seven typically-developing peers. We used G-Power software for all estimates with power of 0.9.

Our primary hypotheses are that support and stabilization costs are elevated in children with cerebral palsy compared to typically-developing peers. To test these hypotheses, for each participant we will calculate the walking energy in each condition. We then test the impact of vertical and lateral support using linear regression models, comparing how the walking energy changes with support. In this model, walking energy is the net dimensionless walking cost, and support assistance represents the levels of either vertical or lateral support. Secondarily, we will use linear multiple regression models to evaluate the impact of participant characteristics on support and stabilization costs. In this model, cost is the net dimensionless walking cost, assistance represents the four levels of either vertical or lateral support assistance, group represents the cerebral palsy and typically-developing cohorts, and characteristics include participant characteristics. We will evaluate whether the coefficient for group is significant, indicating the effect of support is different between groups. Participant characteristics for the regression model will include age, sex, body mass index, and minimum knee flexion during stance.

Table 1: Variable definitions

Variable	Description
Net Dimensionless Walking Cost	The energy consumed per unit time during walking, normalized for body size, calculated as the difference between walking cost and resting cost.
Support Cost:	The change in net dimensionless walking cost at maximum vertical support assistance compared to no assistance condition.
Stabilization Cost	The reduction in net dimensionless walking cost at maximum lateral stabilization assistance compared to no assistance condition.

REFERENCES

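### The secondary regression pools four walking-cost values per child with no participant term stated, and its group coefficient does not test whether the effect of support differs

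*Combined protocol and SAP*

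**What the plan says.** All of this is in the Statistical Analysis section, in the paragraph before Table 1.

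- Aim of the model: "Secondarily, we will use linear multiple regression models to evaluate the impact of participant characteristics on support and stabilization costs".
- Outcome and rows: "cost is the net dimensionless walking cost, assistance represents the four levels of either vertical or lateral support assistance". That is one row per child per level.
- Other terms: group (cerebral palsy or typically developing) and characteristics. "Participant characteristics for the regression model will include age, sex, body mass index, and minimum knee flexion during stance".
- Inference on group: "We will evaluate whether the coefficient for group is significant, indicating the effect of support is different between groups".

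Table 1 defines support cost as "The change in net dimensionless walking cost at maximum vertical support assistance compared to no assistance condition", and stabilization cost likewise as a difference between maximum and no lateral assistance. Both are one number per child.

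The text names no participant effect, repeated-measures structure, cluster-robust error or product term. Ordinary least squares is therefore an inference from the terms listed.

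The first regression in the same paragraph is a separate matter. It starts from the statement that "for each participant we will calculate the walking energy in each condition", has no child-level covariate and may be fitted child by child. No error inflation is claimed there.

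**The concern.** There are two faults.

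**Wrong contrast.** The question is what changes the support cost, a within-child difference. The model's outcome is the level of walking cost. A main effect of group or of a characteristic on that level says who spends more energy on average, not who gains more from assistance. The plan already expects a group difference in level. The Background describes walking cost in cerebral palsy as "on average over two times higher than for typically-developing individuals", and the sample-size paragraph says "the difference in fixed cost between children with cerebral palsy and typically-developing peers from our retrospective analyses supports this effect size". A significant group coefficient is thus likely even if support helps both groups equally, and the SAP would report it as a difference in the effect of support.

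**Correlated rows.** Age, sex and BMI are fixed within a child. With 28 children and four levels there are 28 × 4 = 112 rows per aim, but only 28 independent units for these covariates. Treating the rows as independent makes the standard errors too small.

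This is the plan's only analysis of which characteristics change support and stabilization cost. Its group result could also contradict the primary t-test purely as an artefact.

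**Working it through.** **1. The plan's own figure.** Inputs from the sample-size paragraph: effect size 1.5, alpha 0.05, power 0.9, 3:1 allocation, independent t-test. Noncentrality = 1.5 × √(21 × 7 / 28) = 1.5 × √5.25 = 3.44 on 26 df, which gives exact two-sided power of 0.911. With 18 + 6 children it is 0.860. So 21 + 7 reproduces. That test uses one value per child and is not affected.

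**2. What the group coefficient measures.** For child i at assistance level A, the stated terms give

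E(cost) = b0 + b1·A + b2·group + b3·characteristic.

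The change from no assistance to maximum is b1·A_max for every child, whatever the group or characteristic. This model cannot express a group difference in support cost; b2 is the group difference in cost level. Adding b4·group·A makes the group difference in support cost b4·A_max, so the relevant coefficient is the interaction.

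**3. Simulation set-up.** The documents give no intraclass correlation (ICC), so 0.3 to 0.9 is assumed. Other assumptions: 21 + 7 children, four equally spaced levels, total variance 1, a random child intercept with variance equal to the ICC, and one value per child for each characteristic unless stated. There are 20,000 runs per setting unless stated.

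**4. Characteristic tests, no true effect, nominal 5%, ordinary regression.** For a child-level covariate the true variance exceeds the assumed one by 1 + (4 − 1) × ICC, so approximate size = 2 × [1 − Φ(1.96 / √(1 + 3·ICC))]. At ICC 0.3 this is 2 × [1 − Φ(1.96 / √1.9)] = 15.5%.

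| ICC | 0.3 | 0.5 | 0.7 | 0.8 | 0.9 |
|---|---|---|---|---|---|
| 1 + 3·ICC | 1.9 | 2.5 | 3.1 | 3.4 | 3.7 |
| Analytic size, before covariates | 15.5% | 21.5% | 26.6% | 28.8% | 30.8% |
| Simulated, age | 16.8% | 23.6% | 28.9% | 32.7% | 34.9% |
| Simulated, any of four characteristics | 50.0% | 63.9% | 72.7% | 77.0% | 79.8% |

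Sex and BMI behave like age. Four valid independent tests would give 1 − 0.95⁴ = 18.5% for any of four. If half of knee flexion's variance is within child, its own rate is 10.5% to 21.7% and the any-of-four rate 46.5% to 76.1%.

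**5. Group coefficient, identical support effect in both groups.** Percentage significant at ICC 0.3 / 0.5 / 0.7 / 0.9, for assumed differences in average cost:

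| Difference | Ordinary regression | Child means (valid errors) |
|---|---|---|
| 0.5 SD | 55.7 / 55.9 / 57.0 / 58.2 | 31.1 / 24.6 / 21.4 / 18.0 |
| 1.0 SD | 94.7 / 92.2 / 90.4 / 89.0 | 83.1 / 71.4 / 62.9 / 55.2 |
| 1.5 SD | 99.8 / 99.7 / 99.4 / 98.7 | 99.0 / 96.6 / 92.9 / 87.8 |

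A group test on the Table 1 difference rejects in 4.7% to 5.2% throughout. Correct standard errors alone therefore do not cure the wrong contrast.

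The reverse also fails. With a true 1.5 SD difference in support cost and equal average cost, the group coefficient is significant in only 21% to 36% of studies (ICC 0.5 to 0.9; 2,000 to 4,000 runs). That is about its own false-positive rate; the t-test has about 91% power.

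**6. Would adding only the interaction do?** No. In ordinary regression the error term carries between-child variance that cancels from within-child changes. At ICC 0.3, 0.5, 0.7, 0.8 and 0.9, group × assistance rejects a true null in 2.3%, 0.9%, 0.1%, 0.01% and 0%. Its power for a 1.5 SD difference in support cost is 90%, 82%, 59%, 33% and 5%. If child-specific slopes make up 80% of the variance of the cost difference, null rejection is instead 9.2% at ICC 0.3, falling to 0.7% at 0.9. A random intercept without a random slope then rejects in 18.8% to 19.6%.

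**7. One row per child.** Regressing the Table 1 difference on group and the four characteristics (28 − 6 = 22 residual df) has type I error of 4.8% to 5.2% in every case and power of 84.8% to 85.8% for a 1.5 SD group difference.

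**The case against.** The strongest reply is that the paragraph reads like the key to a displayed equation that did not survive in the text available here. That equation might contain a participant term or a group × assistance product, with the group coefficient being loose wording for the product. This stands as a limit on certainty: the absence is of any stated term. It does not rescue the sentence on group. With an interaction fitted and no assistance coded 0, the plain group coefficient is the difference in unassisted cost, and it was significant in 96% to 97% of simulated studies with identical support effects and a 1.5 SD difference in level. If per-child support cost was the intended outcome, the stated outcome and the four-level regressor are wrong instead.

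The sizes rest on assumptions. At ICC 0.1 the rates fall to 8% to 9% per test and 29% for any of four, though so low a correlation is unlikely for repeated measures on one child. Part of the any-of-four rate is ordinary multiplicity. The text does not say whether no assistance is one of the four levels; with five rows per child, the age test's error is 27% to 41% for ICC 0.5 to 0.9. The Background's doubling of cost is not stated for net dimensionless cost at the study's fixed speed, so the SD differences above are illustrative.

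Finally, the analysis is secondary, and the primary t-tests already compare the groups correctly. That is right, and it limits the severity.

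**Conclusion.** The point holds, as something that should be fixed in a secondary analysis. That the group coefficient answers a different question follows from the stated outcome and terms and needs no assumed correlation. How often it misleads depends on the true difference in cost level: 56% to 58% of studies at 0.5 SD and 89% to 95% at 1 SD under ordinary regression. The inflation of the characteristic tests, to about 16% to 35% each, rests on ordinary regression being intended and on an ICC of 0.3 to 0.9. The direction holds for any positive within-child correlation, for covariates fixed within a child. Confidence is medium, because the model's form is inferred from a verbal description.

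**What to change.** Replace only the secondary model in the Statistical Analysis section.

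- **Preferred.** For each aim, regress each child's Table 1 support or stabilization cost (28 values) on group, age, sex, BMI and one knee-flexion value per child, naming the condition that value comes from. The existing sentence about the group coefficient is then true as written.
- **Alternative.** Fit a linear mixed model to all levels with a participant random intercept and random assistance slope, Kenward-Roger or Satterthwaite degrees of freedom, and group × assistance and characteristic × assistance terms. Read group and characteristic effects from the interactions. If the slope variance cannot be estimated, fall back on the child-level regression, not on a random intercept alone.
- Say whether the first regression is fitted per child. If it pools children, give it the same participant terms.
- State whether no assistance is one of the four levels, and that the independent t-tests remain primary.

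The cost is SAP wording and standard software. Standard errors for child-level terms will be wider. The preferred model leaves the intermediate levels unused; the mixed model uses them. Adjusted power for a 1.5 SD group difference is about 85%, against 91% for the unadjusted t-test, which is a reason to keep the t-test primary.

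### The secondary regression tests the group coefficient, which measures a difference in walking-cost level, and reads it as a difference in the effect of support

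*Combined protocol and SAP*

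**What the plan says.** The second paragraph of the Statistical Analysis section introduces the secondary analysis: "we will use linear multiple regression models to evaluate the impact of participant characteristics on support and stabilization costs". It then defines the model's terms: "cost is the net dimensionless walking cost, assistance represents the four levels of either vertical or lateral support assistance", plus group (CP or TD) and characteristics. No product of group and assistance is mentioned. The decision rule is: "We will evaluate whether the coefficient for group is significant, indicating the effect of support is different between groups". The covariates are listed: "Participant characteristics for the regression model will include age, sex, body mass index, and minimum knee flexion during stance".

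Table 1 defines support cost as a within-child contrast: "The change in net dimensionless walking cost at maximum vertical support assistance compared to no assistance condition". Stabilization cost is the matching reduction under lateral assistance.

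Two other places bear on the point. The first paragraph of the Statistical Analysis section gives the between-group test: "Independent sample t-tests will be used to compare the support and stabilization costs between groups". The Background says that in people with CP "the energetic cost of walking is significantly increased, on average over two times higher than for typically-developing individuals".

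**The concern.** The outcome is a level, with one value per child per condition. The quantity of interest is a change between conditions. A group coefficient on a level outcome compares how costly walking is in the two groups. It does not compare how much that cost moves when support is added.

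Under the stated rule, the secondary analysis could report that support acts differently in CP only because walking with CP costs more overall, which the protocol takes as known. It could then seem to confirm or contradict the t-test while answering another question. Likewise, a characteristic linked only to overall cost would be reported as influencing support or stabilization cost.

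**Working it through.** **The plan's own figure.** Effect size 1.5, alpha 0.05, 21 CP and 7 TD. The noncentrality is 1.5 × √(21 × 7 / 28) = 1.5 × √5.25 = 3.44 on 26 df. Two-sided power is 0.911, and 21 + 7 is the smallest 3:1 design that reaches 0.90. The sample size reproduces, and it belongs to the t-test on the costs.

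**What the coefficient means.** Write A for assistance, G for group (CP = 1) and X for the characteristics.

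- As described: E[cost] = b0 + b1·A + b2·G + b3′X. The effect of moving from A = 0 to A = a is b1·a in both groups by construction. b2 is the adjusted CP − TD difference in level.
- With a product term: E[cost] = b0 + b1·A + b2·G + b3′X + b4·A·G. The effect is b1·a in TD and (b1 + b4)·a in CP, so the difference is b4·a. b2 is now the level difference at A = 0.

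In neither form does b2 measure a difference in the effect of support. The same holds for b3: without X-by-A products it describes cost level.

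**How often the rule misleads.** The documents do not give the cost ratio at Gross Motor Function Classification System (GMFCS) Level II and speed 0.26, the between-child coefficient of variation (CV), the noise or the level spacing. All are assumed:

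- TD cost 1; CP cost 1.2, 1.5 or 2.0
- between-child CV 40% or 20% of the group mean
- mean support cost 0.1 in **both** groups, between-child slope SD 0.10, trial noise SD 0.05
- four equally spaced levels, four covariates, 2,000–3,000 runs per scenario

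Share of runs with a significant group coefficient, CV 40% to 20%:

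| CP/TD cost ratio | Least squares on 112 rows (28 × 4) | One mean per child |
|---|---|---|
| 2.0 | 99–100% | 84–100% |
| 1.5 | 88–100% | 43–96% |
| 1.2 | 51–80% | 12–38% |

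Regressing per-child slopes, or the Table 1 costs, on group and covariates rejected in 4–6% throughout. Unequal spacing (0, 0.1, 0.2, 1) at 2.0-fold left the rates unchanged. If knee flexion also differs by 1.5 SD between groups, 2.0-fold gives 95–100% and 66–99%.

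The least-squares column also contains a separate problem. Ignoring the four rows per child rejects 37–38% even with no cost difference. The right-hand column isolates the present point.

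**In SD units, without covariates.** A valid between-child test of level at 21/7 rejects with probability 0.20, 0.60, 0.91 and 0.99 for level differences of 0.5, 1.0, 1.5 and 2.0 SD, whatever support does.

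**The reverse error.** Assume SDs of 1 (intercept), 0.5 (slope) and 0.3 (residual). The SD of the change score is √(0.5² + 2 × 0.3²) = 0.656. Let the slopes differ by 1.5 of these SDs, with average levels balanced. The group term then rejects in 5% of runs and the slope comparison in 92%.

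**Characteristics.** Let knee flexion correlate 0.6 with cost level and not with support cost (assumed; 2.0-fold, CV 20%). Its main effect is significant in 87% of participant-level fits, against 5% for its effect on the slope.

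**The case against.** The strongest reply is that the description reads like the legend to an equation that is not in the available text, and the equation may contain the product term. That is possible. But the sentence still names the group coefficient, which would then be the level difference at zero assistance.

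A second reply is that the outcome may be meant to be support or stabilization cost, as the stated aim suggests. The sentence would then be right. The plan, however, defines cost as walking cost and makes the assistance levels a predictor. If change scores are intended, the text still has to say so, and that is a legitimate repair.

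Third, the rates depend on assumed inputs, and the two-fold figure is a general background statement, not specific to GMFCS Level II at this speed. This stands: at 1.2-fold the participant-level rate is 12–38%, well below the 2.0-fold range.

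Fourth, the 4–6% for per-child slopes assumes equal slope spread in the groups. With slope SDs of 0.20 in CP and 0.10 in TD it falls to 1.6%; reversed, it rises to 11.9%. This also stands, but the equal-variance form of the planned t-test is exposed in the same way.

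Finally, the analysis is secondary. That limits the consequence but does not correct the reading.

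**Conclusion.** The decision rule is wrong as written. This follows from the model's algebra and needs no assumption about variances or about the unseen equation. How often it would mislead does depend on assumptions: with equal support costs, from 12% of trials (1.2-fold cost, CV 40%) to practically all (2.0-fold, CV 20%) in a fit that respects the clustering by child. It can also miss a real difference in the effect of support.

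The fault is confined to the secondary regression, including its reading of age, sex, body mass index and knee flexion. The t-tests on support and stabilization costs target the right contrast, and their sample size is sound. It should be fixed before analysis, but it does not undermine the trial's main comparison.

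**What to change.** Either of two repairs makes the stated conclusion follow from the test.

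1. **Keep walking cost as the outcome.** Suggested wording: *We will test the group-by-assistance interaction, and assistance-by-characteristic interactions for age, sex, body mass index and minimum knee flexion, in a mixed model with a participant random intercept and a random slope for assistance, fitted separately for vertical and lateral assistance.* A random intercept alone is not enough: its interaction test rejected 5%, 8%, 15% and 22% at assumed between-child slope SDs of 0, 0.05, 0.10 and 0.20 (2.0-fold, CV 30%). State a small-sample degrees-of-freedom method, since a normal reference where 22 df apply gives about 6.3%. If the model does not converge, regress each child's slope over the four levels on group and characteristics. This route assumes a linear response across the levels.
2. **Make the Table 1 cost the outcome.** Regress support or stabilization cost on group and characteristics. The group coefficient then means what the plan says. This is simpler and matches Table 1, but it uses two of the four levels and is a different estimator.

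The cost is SAP wording and, for the first repair, five interaction terms and a random slope per model. No new data or larger sample is needed. The drawback is precision with 7 TD children. At effect size 1.5, power for group is about 85% with four covariates unrelated to group (22 df) and about 71% if knee flexion differs by 1.5 SD (assumed), against 91% for the unadjusted t-test.
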